4. C-SSRS
5. Routine serum chemistries with liver function tests
6. Routine hematology tests with coagulation tests

Statistical Considerations**Data Analysis**

This is a within-subject, controlled open-label study seeking to determine the safety and tolerability of EPI-589 in patients with PD as well as to determine if EPI-589 can alter the biochemical signature of PD as assessed by peripheral blood biomarkers, CNS biomarkers, brain imaging biomarkers, and urine biomarker analysis. In addition, data on a number of disease-relevant clinical measures will be collected.

Space Intentionally Left Blank

II. SCHEDULE OF ASSESSMENTS AND DOSING SCHEDULE

Tests	-2 to -1 Months		Day0		Month 1	Month 2	Month3 End of Treatment Visit	Post-Treatment Follow-up
	Screening	Run-in (upto 30 days from screening2)						
Informed consent				Day 1 First Dose				
Inclusion/Exclusion criteria								
Past Medical history								
Previous genetic testing review								
Physical exam & Vital signs	b							
Height & weight	g		-					
12-lead ECG			-					
Hematology (including coagulation panel)			a,f					
Serum Chemistry			a,f					
Pregnancy test"								
C-SSRS								
Montreal Cognitive Assessment								
DaTscan (for idiopathic subjects)								
Revised Hamilton Rating Scale for Depression								
Subject enrolls in study		X						
Fasting blood-based glutathione cycle biomarkers								
Fasting Lumbar puncture (CNS biomarkers)								
Fasting Urine-based biomarkers								
MDS-UPDRS								
Timed motor tests (for subjects on dopa-amine therapy)								
NMSS, PDQ-39, EQ-5D								
BDI, MADRS								
Dmg plasma concentration ^o					c	c		
AE/SAE assessment	•	•	•		d	d	-	
Concomitant medications assessment					d	d	-	
Post-Treatment Assessments*								•

a. Screening values can be used if done within one month of baseline and if completed under fasted conditions

b. Female subjects of childbearing potential must have a negative pregnancy test.

c. Full plasma concentration profile will be obtained at Time= 0, and 0.5, 1, 2, 4, 6, 8, and 12 hours after dosing from the first 10 subjects to complete 1 month of therapy at each site. 12 hour PK can be obtained at time 0.

d. Month 2 assessments can be done by telephone. Any new AEs and associated concomitant medications reported at Month 3 must be followed for 30 days; this follow up may be conducted by telephone.

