9. MDS-UPDRS
10. MoCA
11. DaTscan (for idiopathic subjects only)
12. Revised Hamilton Rating Scale for Depression
13. SAE assessments
14. Concomitant medications assessment (last 60 days prior to enrollment)

*Breast exam is at screening physical exam only.

** Height is measured at screening visit only.

***Screening values can be used if done within one month of baseline and if completed under fasted conditions

A1. Run-in Assessments

If the subject is eligible for the study following all screening procedures and is still willing to participate in the study, the subject must return to the clinic within one month for Run-in assessments. These will be performed 30 days (\pm 3 days) prior to baseline after eligibility is confirmed and subject is enrolled in the study. Run-in evaluations consist of the following:

1. Fasting blood-based glutathione cycle biomarkers
2. Fasting CNS biomarkers (lumbar puncture)
3. Fasting urine biomarkers
4. Timed motor tests (for subjects on dopamine therapy)
5. AE/SAE assessments
6. Concomitant medications review

B. Treatment Phase

After the Run-in phase, the subject must return to the clinic within 30 days (± 3 days) for baseline assessments. In-clinic study visits are scheduled at Month 1 and Month 3. The Month 2 study assessments can be conducted via telephone. End of treatment assessments will be conducted at the Month 3 study visit. Pharmacokinetic sampling takes place at Month 1 and Month 3. The baseline and all subsequent laboratory assessments should be obtained under fasting conditions.

B1. Baseline Assessments

The following will be assessed or performed at this visit.

1. Physical examination including vital signs
2. Height and weight*
3. 12-Lead ECG*
4. Fasting blood-based GSH cycle biomarkers
5. Fasting urine-based biomarkers
6. Laboratory assessments for hematology, coagulation and serum chemistry*
7. Urine pregnancy test (females of child bearing potential)
8. C-SSRS (Columbia Suicide Severity Rating Scale)

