9. MDS-UPDRS

10. Pharmacokinetics**: a full plasma drug concentration profile will be obtained from the first 10 subjects to complete 1 month of therapy at each site at: Time = 0, and 0.5, 1, 2, 4, 6, 8, and 12 hours after dosing. 12 hour time point may be obtained at 0 hour.

11. AE/SAE assessments

12. Concomitant medications review

* The laboratory assessments should be obtained under fasting conditions.

- Month 2 Visit (Day 57 ± 3 days)

Month 2 assessments can be conducted by telephone and must include review of:

1. AE/SAE assessments
2. Concomitant medication

- Month 3 Clinic Visit (Day 85 ± 3 days)

The following will be assessed or performed at the Month 3 clinic visit:

1. Physical examination including vital signs
2. Height and weight
3. 12-lead ECG
4. Laboratory assessments for hematology, coagulation, and serum chemistry*
5. Urine pregnancy test (females of child bearing potential)

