6. C-SSRS
7. Fasting blood-based GSH cycle biomarkers
8. Fasting urine-based biomarkers
9. Fasting CNS biomarkers

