14. NMSS, PDQ-39, EQ-5D
15. BDI, MADRS
16. Timed motor tests (for subjects on dopamine therapy)

* The laboratory assessments should be obtained under fasting conditions.

B3. Pharmacokinetics**

Plasma concentration samples will be collected from 20 subjects (10 idiopathic and 10 with genetically defined subtypes) at the following time points:

- Month 1 (Day 29 ± 3 days): 0 hour and 0.5, 1, 2, 4, 6, 8, and 12 hours post-dose
- Month 3 (Day 85 ± 3 days): 0 hour and 0.5, 1, 2, 4, 6, 8, and 12 hours post-dose

** 12 hour PK can be obtained at time 0

The pharmacokinetics samples collection will be monitored as subjects are enrolling and sponsor will alert each principal investigator once the required samples for each subtype are obtained.

B4. Early Termination Study Visit

Subjects who terminate from the study after receiving first dose and prior to the completion of all scheduled visits should have the end of treatment visit assessments completed as soon as possible.

C. End of Treatment Visit

End of treatment visit takes place at Month 3 (Day 85 ± 3 days) and includes the assessments listed in Section **VB2** Study Visit Assessments.

Subjects who have an ongoing AE at the time of study completion will be followed for up to 30 days, until the event resolves, or until the Sponsor and the Investigator agree that further follow-up is not medically necessary.

D. Post-Treatment Follow-up

Post-Treatment Follow-up will be at least 10 days and up to 30 days after last dose, with AE/SAE and concomitant medication assessments conducted by telephone. Additional assessments to be determined at Investigator discretion.

E. Unscheduled Visits

If a subject returns to the clinic outside of the normal study visit windows, assessments will be made at the Investigator's discretion. All study relevant unscheduled visit assessments will be recorded in the case report form (CRF) using the supplemental visit CRF pages.

F. Concomitant Medication

Any medication taken by a subject ≤ 60 days prior to enrollment and during the course of the study and the reason for use of the medication will be recorded on the CRF. During screening, each subject will be instructed to report the use of any medication to the Investigator. Subjects

will also be instructed about the importance of not taking any medication throughout the study (including over-the-counter [OTC] medications) without consulting the Investigator.

G. Prohibited Medications

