In the US, all fatal or life-threatening suspected unexpected serious adverse events assessed as possibly or probably related to study drug by the Sponsor must be reported to the FDA as soon as possible (i.e., by telephone or facsimile transmission), but no later than 7 calendar days after first knowledge by the Sponsor that a report qualifies as a suspected unexpected fatal or life-threatening reaction. All unexpected serious adverse events, other than fatal or life-threatening, assessed as possibly or probably related to study drug by the Sponsor must be reported to the FDA within 15 calendar days from the day the Sponsor determines that the information qualifies as a SUSAR.

In the UK, the Sponsor or trial investigator must act immediately or at least within 24 hours after becoming aware of a SUSAR by informing the MHRA's Clinical Trial Unit by telephone. The MHRA must then be informed in writing within 3 days of the incident. All SUSARs originating in the UK or originating outside the UK involving the same medicinal product are to be reported. Fatal or life-threatening SUSARs are to be reported as soon as possible, but no later than after 7 days. Any additional relevant information must be sent within 8 days of the report. Non-fatal or non-life-threatening SUSARs are to be reported as soon as possible but no later than 15 days after becoming aware of the reaction.

C8. Follow-up Report

If an SAE has not resolved at the time of the initial report, a follow-up report including all relevant new or reassessed information (e.g., concomitant medication, medical history) should be submitted to the IRB/ IEC . All SAEs should be followed until either resolved or stable.

C9. Dose Modification Guidelines

In the event that any patient develops elevated INR \geq grade 2 in severity ($> 1.5-2.5 \times \text{ULN}$) per CTCAE criteria version 4.0 thought to be related to treatment with EPI-589, administration of EPI-589 will be reduced by 1/2 to 50 percent of the starting dose. Should the INR toxicity not resolve to at least grade 1 in severity within two weeks of the initial dose reduction, administration of EPI-589 may either be further reduced or discontinued.

Once a patient's dose is reduced due to elevated INR thought to be related to study drug administration, their dose should not be re-escalated.

D. Medical Emergencies

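### The end-of-treatment lumbar puncture has no INR condition, although X.C9 provides for drug-related INR elevation and the only scheduled INR after Month 1 is drawn at the puncture visit

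*Protocol*

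**What the plan says.** All references are to the current protocol text (Amendment 5.0).

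- **The puncture.** Item 9 of the Month 3 list in VI.B2 is "Fasting CNS biomarkers". The matching row in the Section II schedule reads "Fasting Lumbar puncture (CNS biomarkers)", and the run-in list in VI.A1 also gives lumbar puncture as the method.
- **Early termination.** Under VI.B4, subjects who leave after the first dose and "prior to the completion of all scheduled visits should have the end of treatment visit assessments completed as soon as possible". VI.C makes the end-of-treatment visit the Month 3 visit, so the puncture is included.
- **INR rule.** X.C9 halves the dose if INR of grade 2 or more (above 1.5 x ULN) is thought related to EPI-589. It continues: "Should the INR toxicity not resolve to at least grade 1 in severity within two weeks of the initial dose reduction", then "administration of EPI-589 may either be further reduced or discontinued". It does not mention the puncture.
- **INR sampling.** "Laboratory assessments for hematology, coagulation, and serum chemistry" are listed at Month 1 and Month 3, and VII.D2 includes INR in the coagulation panel. For the contact in between, "Month 2 assessments can be conducted by telephone and must include review of" adverse events and concomitant medication; no laboratory test is listed.

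**The concern.** X.C9 recognises INR elevation as something the drug might cause and that might not settle promptly, but uses INR only to set the dose. The one invasive research procedure on treatment, for which INR matters most, is not tied to it. The puncture serves a secondary biomarker endpoint and is not part of the subject's care. That a puncture at a raised INR carries a risk of spinal bleeding is a general clinical premise; the protocol gives no figure for it.

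Two situations follow from the text as written. A subject stopped for unresolved INR who also leaves the study becomes due for an elective puncture promptly, with no instruction to defer it. And an INR rise that starts after Month 1 is first measured, on schedule, at the visit where the puncture is done, with no instruction to see the result beforehand. X.D2 relies on laboratory tests to reveal drug effects before they matter clinically; a result that need not be read before the needle does not serve that purpose.

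**Working it through.** The plan has no figure of its own to reproduce. The check is a reading of the provisions together, plus visit-window arithmetic.

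**1. Is there an INR condition anywhere?**

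| Place | What it contains | INR condition on the puncture? |
|---|---|---|
| V.D2, 15 exclusion criteria | limits for liver tests and creatinine | no |
| VI.G, prohibited medications | antioxidant vitamins, other trials | no |
| VI.B2 Month 3 list, item 9 | the puncture | no |
| VI.B4 and VI.C | the Month 3 assessments for early terminators | no |
| VII.D2, laboratory evaluations | INR and platelets measured; significant abnormalities repeated | no link to the puncture |
| VII.D3, dose-limiting toxicity | liver, renal and CPK rises | no |
| VII.E, sample collection | collection and handling details supplied separately | not stated |
| X.C9 | INR rule | dosing only |

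**2. How old is the last scheduled INR at the puncture?**

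Month 1 window: Day 29 ± 3 = Day 26 to 32. Month 3 window: Day 85 ± 3 = Day 82 to 88.

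- Shortest gap: 82 − 32 = 50 days.
- Longest gap: 88 − 26 = 62 days.

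So there are two scheduled on-treatment draws. Unless the Month 3 result is awaited, the value in hand is 50 to 62 days old in a subject with no known INR problem.

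**3. Where does the two-week judgement fall if INR is raised at Month 1?**

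Assume the dose is halved on the day of the Month 1 visit. This is the earliest case, since the result may arrive later.

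- Judgement: 26 + 14 = Day 40 to 32 + 14 = Day 46.
- From judgement to the Month 3 puncture: 82 − 46 = 36 days to 88 − 40 = 48 days.

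Unresolved at that judgement means INR above 1.5 x ULN on that day. INR at the later puncture is not known.

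**4. Three routes to an unconditioned puncture.**

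- Drug stopped for unresolved INR and the subject leaves the study: puncture due under VI.B4, soon after a known elevation.
- Further reduced dose, or off drug but still in the study: scheduled Month 3 puncture, 36 to 48 days after the judgement under the assumption in step 3.
- INR normal at Month 1 and raised later: first scheduled measurement is at the puncture visit.

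In the first two the elevation is known to the investigator. In the third it is not, unless the result is read first.

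**The case against.** The strongest case on the other side has five parts.

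- **No signal.** X.C9 is conditional. The dose-limiting animal findings in III.D1 are hemolysis and muscle, kidney, liver and lymphoid effects, and both Phase 1 studies in III.D2 report no clinically relevant laboratory change. Superseded versions of the rule (Amendments 3.0 and 4.0) attributed the INR rise to another compound, EPI-743, which suggests carried-over wording. This stands: a reader might infer that EPI-589 is known to raise INR, and the protocol does not show that. What remains is that the current text writes a rule for the event and leaves the puncture out of it.
- **Judgement and repeat testing.** An investigator who knows INR is raised would usually hold the puncture. VII.D2 calls for repeat and additional tests, VII.D1 asks that clinically significant abnormal measurements be repeated, and the two-week test in X.C9 itself needs an INR between scheduled visits. This largely answers the first two routes. The 36 to 48 days should therefore not be read as a period without INR monitoring. It does not answer the third route, where there is no known abnormality to follow.
- **Late onset is unsupported.** Mean half-life on multiple dosing was 5.64 to 8.47 hours (III.E), and Month 1 follows four weeks of dosing. Fair, and a reason to expect very few cases; it does not exclude one.
- **VI.B4 compels nothing.** It says *should*, fixes no day, and covers only those leaving the study. A reader might infer that the protocol orders a puncture at a raised INR. It does not; it fails to say that one should wait.
- **Another document may cover it.** VII.E refers to separate instructions, not shown here. They are described as covering the collection, handling, storage and shipment of the marker samples. A pre-puncture check there or in site practice cannot be ruled out, but this protocol does not require one.

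A platelet condition is also tempting. X.C9 concerns INR alone, and no part of the protocol reports a platelet effect, so that extension is not supported.

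**Conclusion.** The point holds for INR. The protocol provides for drug-related INR above 1.5 x ULN that persists after the dose is halved, yet the end-of-treatment puncture, at Month 3 or early termination, has no INR condition, and the only scheduled INR after Month 1 comes from the same visit with no instruction to read it first. This is a procedural safety rule, not something a statistical analysis plan would supply.

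The size is small. Few subjects would be affected and the number cannot be estimated from the protocol. The day counts describe timing, not risk, and assume visits within their windows. The conclusion rests on the premise that an elective puncture at a raised INR is undesirable, and on the protocol text alone. It is a minor safety amendment.

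**What to change.** In the Month 3 list of VI.B2 and in VI.B4, state that the lumbar puncture is done only after an INR from that visit, or from the few days before it, has been reviewed and is not above the protocol's own grade 2 threshold of 1.5 x ULN. Otherwise it is deferred until INR resolves, or omitted with the reason recorded. Cross-refer to this rule from X.C9. The platelet count from the same sample may be reviewed as ordinary caution, without presenting it as a response to a drug signal.

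Cost: amendment wording, and a short wait for, or a slightly earlier draw of, a sample the visit already collects. A very few end-of-treatment CSF samples may be lost. Each is 1/40 = 2.5% of the planned 40 subjects, or 1/60 = 1.7% if all 20 additional subjects are enrolled.

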7. A diagnosis of idiopathic PD confirmed by the presence of bradykinesia plus one or both of the following symptoms: rigidity or resting tremor; and with an abnormal DaTscan consistent with a dopaminergic deficit
8. Age 40 to 75 years
9. Within 5 years of diagnosis of Parkinson's disease

For Genetic Subtype Subjects

10. A confirmed diagnosis of PD plus a genetic diagnosis consistent with PD, specifically PINK1, parkin, LRRK2 or other mitochondrial genetic subtype
11. Age 21 to 75 years

Exclusion criteria

1. Allergy to EPI-589 or other components of the EPI-589 tablet formulation
2. Use of antioxidant supplements, specifically vitamins E and C beyond the recommended daily allowance
3. Other Parkinsonian disorders
4. MoCA score of <24
5. Revised Hamilton Rating Scale for Depression ≥ 11
6. Parkinsonism due to drugs or toxins
7. Diagnosis of any other clinically significant neurologic disease that will

confound the assessment of effect of study drug on disease progression

8. Malignancy within past two years
9. Pregnant or plans to become pregnant or breast feeding
10. History of stroke
11. History of brain surgery
12. Hepatic insufficiency with liver function tests (LFTs) > 3 times upper limit of normal
13. Renal insufficiency as defined by creatinine > 1.5 times normal
14. End stage cardiac failure
15. Participation within past 3 months and for duration of study in a trial of a device, drug or other therapy for PD

Treatment
Following study enrollment, baseline assessments will be performed. Subjects will participate in a 30-day run-in phase to establish biomarker and clinical baseline measurements. EPI-589 will then be administered for up to 3 months (85 days \pm 3 days) unless discontinued for safety or tolerability issues. Post-treatment follow-up will be at least 10 days and up to 30 days after last dose.

Efficacy variables

1. Fasting blood-based glutathione biomarkers
2. Fasting CNS biomarkers
3. Fasting urine-based biomarkers

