The following are prohibited while the subject is on study treatment:

1. Use of antioxidants, specifically vitamins E and C beyond the recommended daily allowance. However if the subjects are on high doses of Vitamin E and C and are eligible to participate, they are allowed a 2 weeks washout period prior to enrollment
2. Participation 3 months prior to and for the duration of the study in a trial of a device, drug or other therapy for PD

H. Subject Withdrawals

Subjects receive study treatment until treatment discontinuation for one of the reasons listed below. However, subjects may discontinue study treatment or withdraw their consent to participate in the study at any time without prejudice. The following conditions require subject discontinuation from all study treatment:

1. At their own request or at the request of their legally authorized representative
2. If a subject experiences an adverse event that is deemed related to treatment with EPI-589 and in the Investigator's or the Sponsor's medical judgment continuation of treatment would be detrimental to the subject.
3. At the specific request of a regulatory agency for termination of treatment of an individual subject or all subjects under the protocol
4. Subject participation in another clinical study using an investigational agent or investigational medical device
5. Use of prohibited medications such as vitamins E and C beyond the recommended daily allowance.
6. Refusal of sexually active fertile subjects (excluding subjects who have been sterilized) to use medically accepted methods of contraception
7. If a subject becomes pregnant.
8. Significant noncompliance with the protocol in the opinion of the Investigator or the Sponsor

In all cases, the reason for withdrawal must be recorded in the CRF and in the subject's medical records. If the reason is not known, the subject must be followed to establish whether the reason was due to an AE, and, if so, this must be reported in accordance with the procedures in Section [X.B.](#)

Evaluations should be performed on all subjects who participate but do not complete the study according to protocol. Dropouts may be replaced at the request of the Sponsor. The Investigator will make every effort to contact subjects lost to follow-up.

Every effort will be made to follow subjects who have an ongoing AE at the time of withdrawal until the event resolves, or until the Sponsor and the Investigator agree that further follow-up is not medically necessary.

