Clarification on the difference in meaning between “severe” and “serious”: The term “severe” is often used to describe the intensity (severity) of a specific event (as in mild, moderate, or severe myocardial infarction); the event itself, however, may be of relatively minor medical significance (such as severe headache). This is not the same as “serious,” which is based on the outcome or action criteria usually associated with events that pose a threat to life or functioning. Seriousness (not severity) serves as a guide for defining regulatory reporting obligations.

C3. Non-serious Adverse Event

A non-serious AE is any AE not meeting the SAE criteria.

C4. Definition of Relationship to Study Medication

Association or relatedness to the study medication will be graded as either “probably”, “possibly”, or “unlikely”. Determination of relatedness includes:

PROBABLY – The adverse event:

1. Follows a reasonable temporal sequence from drug administration
2. Abates upon discontinuation of the drug and reappears with re-introduction of the drug
3. Cannot be reasonably explained by the known characteristics of the subject’s clinical state

POSSIBLY – The adverse event:

1. Follows a reasonable temporal sequence from drug administration
2. Could have been produced by the subject’s clinical state or by other modes of therapy administered to the subject

UNLIKELY – The adverse event:

1. Does not follow a reasonable temporal sequence from drug administration
2. Is readily explained by the subject’s clinical state or by other modes of therapy administered to the subject

C5. Definition of Severity

All AEs will be graded if possible by Common Terminology Criteria for Adverse Events (CTCAE) v4.03. The severity of AEs that cannot be graded by CTCAE v4.03 will be categorized as follows:

Grade 1 – Transient or mild discomfort; no limitation in activity; no medical intervention/therapy indicated.

Grade 2 – Moderate limitation in activity, some assistance may be needed; minimal noninvasive medical intervention/therapy indicated.

Grade 3 – Severe limitation in activity, assistance usually required; medical intervention/therapy required; hospitalization or prolongation of hospitalization indicated; disabling.

Grade 4 – Extreme limitation in activity, significant assistance required; urgent medical intervention/therapy required; life-threatening consequences.

Grade 5 – Death

C6. Definition of Unexpected Adverse Event

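### Protocol VI.H item 2 requires stopping EPI-589 for a detrimental adverse event only if that event is also deemed drug-related

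*Protocol*

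**What the plan says.** Section VI.H (Subject Withdrawals) opens with "Subjects receive study treatment until treatment discontinuation for one of the reasons listed below". The next sentence preserves the subject's right to stop or withdraw at any time. The list is then introduced by "The following conditions require subject discontinuation from all study treatment", so its eight items are obligations.

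Item 2 is the only one that an adverse event triggers. It starts "If a subject experiences an adverse event that is deemed related to treatment with EPI-589" and is joined by *and* to a second test: that continued treatment would, in the Investigator's or Sponsor's medical judgment, be detrimental to the subject.

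Four other statements deal with the end of dosing: the Synopsis (Treatment), V.A for the main study, V.A again for the adaptive phase, and V.C1. Each says that EPI-589 is given "unless discontinued for safety or tolerability issues". None of them sets a causality condition.

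X.C4 grades relatedness as *probably*, *possibly* or *unlikely*; there is no grade called unrelated.

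**The concern.** The second test in item 2 already settles the clinical question. Once a physician concludes that further dosing would harm the subject, the cause of the event adds nothing to the decision to stop. Requiring relatedness as well means that the mandatory rule does not apply in some cases where its own harm test is met.

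Causality is also a weak criterion in this trial. The study is open-label with no reference therapy, so relatedness is judged case by case. X.B1 expects many events from the natural history of Parkinson's disease, and X.C4 makes such an explanation a criterion for the lowest grade.

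A hypothetical example is a malignancy found on treatment. Malignancy within two years bars entry (V.D2 item 8), but that is an eligibility criterion and not a stopping rule. If the malignancy were graded *unlikely* and dosing were judged detrimental, VI.H would not require a stop.

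What is at stake is the protection of the individual subject and the clarity of the instruction to sites. The primary endpoint is not affected by this argument.

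**Working it through.** The plan gives no figure here to reproduce. The check is a reading of the rule against the case in question, followed by a search of the current text (Amendment 5.0) for any other rule that would fill the gap.

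**Step 1. The eight VI.H conditions against this case: an adverse event, dosing judged detrimental, event not deemed related.**

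| Item | Trigger | Requires stopping in this case? |
|---|---|---|
| 1 | Request of the subject or representative | No, unless they ask |
| 2 | Event deemed related *and* dosing judged detrimental | No, the first test fails |
| 3 | Request of a regulatory agency | No, unless the agency asks |
| 4 | Joining another investigational study | No |
| 5 | Prohibited medication | No |
| 6 | Refusal of contraception | No |
| 7 | Pregnancy | No |
| 8 | Significant noncompliance | No; it rests on Investigator or Sponsor opinion, but not about safety |

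One of the eight items concerns an adverse event, and none of the eight covers this case.

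**Step 2. Item 2 as a logical rule.**

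- Related and detrimental: stopping is required.
- Related and not detrimental: stopping is not required.
- Not related and detrimental: stopping is not required. This is the gap.

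**Step 3. Which causality grades fall in the gap.** VI.H does not say which X.C4 grades count as deemed related. X.C7 treats *possibly* and *probably* as related for expedited reporting. If item 2 is read the same way, which is an assumption, 3 − 2 = 1 grade remains: *unlikely*. X.C4 gives two criteria for it: "Does not follow a reasonable temporal sequence from drug administration", and that the event "Is readily explained by the subject’s clinical state" or by another therapy. The *possibly* grade requires a reasonable time sequence and then that the event "Could have been produced by the subject’s clinical state" or have come from another therapy. Many on-treatment events of Parkinson's disease could be graded *possibly* and so pass the first test.

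**Step 4. Other rules that might close the gap.**

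- The Synopsis, V.A (two places) and V.C1 make 4 statements. They permit a stop for any safety reason and require none.
- VI.H, after the list, says that where the reason for a withdrawal is unknown, "the subject must be followed to establish whether the reason was due to an AE". This contemplates withdrawal because of an event without asking about relatedness, but it imposes no duty to stop.
- VII.D3 deems rises in three laboratory groups (LFT, BUN/Cr, CPK) related. These pass the first test of item 2, so they lie outside the gap.
- X.C9 covers a raised INR, but only when thought related to EPI-589. It calls for a dose reduction first, with stopping as a later option.
- X.D tells the Investigator to remove the subject from immediate hazard in an emergency. It does not name stopping EPI-589, and it does not reach detriment short of an emergency.

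**Result.** These provisions narrow the gap. None turns the permission to stop into a requirement when the event is graded *unlikely*.

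**The case against.** A short mandatory list beside a broader discretionary permission is a normal structure, and the two do not contradict each other. An Investigator who has judged dosing detrimental may already stop it under the Synopsis, V.A and V.C1, and no situation has been shown in which that Investigator would be prevented from doing so.

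The remaining group is also small: a non-emergency event, graded *unlikely*, outside the VII.D3 laboratory groups, where the physician judges dosing harmful but does not use the available discretion, and the subject does not ask to stop. Its boundary depends on borrowing the X.C7 convention. The counts in the check describe the wording; they do not measure harm.

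Most of this stands. Stopping is not forbidden, the frequency is unknown, and the extent of the gap rests on an assumption about *deemed related*. It does not remove the point. The opening sentence of VI.H, read literally, ties the end of treatment to the listed reasons and then makes an exception only for the subject's own choice. That sits awkwardly with the wider permission elsewhere. A list of mandatory stops should not omit a case in which the harm that it names has already been judged to exist.

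**Conclusion.** The point holds on the current text. VI.H item 2 makes mandatory stopping depend on causality as well as on detriment, and 0 of 8 conditions requires a stop when an event judged to make dosing detrimental is not deemed related.

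In size it is small. It concerns one of three causality grades, provided that *possibly* counts as related, and it excludes the three VII.D3 laboratory groups. Discretionary stopping, the emergency instruction and the subject's own right to stop limit it further. The protocol gives no rate of detrimental events graded *unlikely*, so no expected number of subjects can be stated.

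The reading of the text is certain; the practical consequence is unquantified. It is an optional improvement to a participant-protection rule.

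**What to change.** In VI.H item 2, replace the clause requiring that the event be deemed related with wording such as *regardless of its assessed relationship to EPI-589*, and keep the clause on the Investigator's or Sponsor's medical judgment unchanged. Mandatory stopping then follows the judgment that the rule already calls for, and VI.H agrees with the Synopsis, V.A and V.C1.

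The cost is one reworded phrase, with no extra visits, procedures or subjects. VI.B4 already asks for end-of-treatment assessments in subjects who terminate early.
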